5. INVESTIGATIONAL MEDICINAL PRODUCTS

5.1. Randomization, Blinding and Treatment Codes

Subjects will be assigned a screening number at the time of consent. **Randomization and Day 1 visits cannot occur until the Investigator has received the results of the screening genotype report and subject eligibility has been confirmed.**

Once eligibility has been confirmed and prior to or during the Day 1 visit, the Investigator or designee will randomize the subject using the Interactive Web Response System (IWRS). Once a subject number has been assigned to a subject, it will not be reassigned to any other subject. The subject number assignment and randomization may be performed up to 3 days prior to the in-clinic Day 1 visit provided that all screening procedures have been completed and subject eligibility has been confirmed.

Subjects will be randomized in a 1:1 ratio to Treatment Group 1 or Treatment Group 2.

Randomization will be stratified by HIV-1 RNA level ($\leq 100,000$ copies/mL, $> 100,000$ to $\leq 400,000$ copies/mL, or $> 400,000$ copies/mL) at screening, CD4+ cell count (< 50 cells/ μ L, $50 - 199$ cells/ μ L, or ≥ 200 cells/ μ L) at screening and region (US vs. Ex-US) at randomization.

The IWRS will assign study drug bottle numbers of blinded FDC of GS-9883/F/TAF + Placebo to match DTG + F/TAF FDC, or DTG + F/TAF FDC + Placebo to match FDC of GS-9883/F/TAF at each study visit for each subject.

At the End of Blinded Treatment Visit the IWRS will assign open label GS-9833/F/TAF/FDC

5.1.1. Procedures for Breaking Treatment Codes

In the event of a medical emergency where breaking the blind is required to provide medical care to the subject or in the case of pregnancy that occurs while on study drug, the investigator may obtain treatment assignment directly from the IWRS system for that subject. Gilead strongly recommends but does not require that the investigator contact the Gilead medical monitor before breaking the blind. Treatment assignment should remain blinded unless that knowledge is necessary to determine subject emergency medical care or in the event of pregnancy that occurs while on study drug. The rationale for unblinding must be clearly explained in source documentation and on the electronic case report form (eCRF), along with the date on which the treatment assignment was obtained. The investigator is requested to contact the Gilead medical monitor promptly in case of any treatment unblinding.

Blinding of study treatment is critical to the integrity of this clinical trial and therefore, if a subject's treatment assignment is disclosed to the investigator, the subject will have study treatment discontinued. All subjects will be followed until study completion unless consent to do so is specifically withdrawn by the subject.

Gilead Pharmacovigilance and Epidemiology (PVE) may independently unblind cases for expedited reporting of suspected unexpected serious adverse reactions (SUSARs).

5.2. Description and Handling

5.2.1. Formulation

5.2.1.1. GS-9883/Emtricitabine/Tenofovir alafenamide (GS-9883/F/TAF) 50 mg/200 mg/25 mg and Placebo to Match Tablets

GS-9883 50 mg/Emtricitabine 200 mg/Tenofovir alafenamide 25 mg tablets are capsule-shaped, film-coated purplish-brown, debossed with "GSI" on one side of the tablet and "9883" on the other side of the tablet. Each tablet core contains 50 mg of GS-9883, 200 mg of emtricitabine, and 25 mg of tenofovir alafenamide. In addition to the active ingredients, the GS-9883/F/TAF tablets contain croscarmellose sodium, magnesium stearate, and microcrystalline cellulose. The tablet cores are film-coated with iron oxide red, iron oxide black, polyethylene glycol, polyvinyl alcohol, talc, and titanium dioxide.

The placebo to match (PTM) GS-9883/F/TAF tablets are capsule-shaped, film-coated purplish-brown, debossed with "GSI" on one side of the tablet and "9883" on the other side and are identical in physical appearance to GS-9883/F/TAF tablets. The placebo tablets contain microcrystalline cellulose, lactose monohydrate, croscarmellose sodium and magnesium stearate. The tablet cores are film-coated with iron oxide red, iron oxide black, polyethylene glycol, polyvinyl alcohol, talc, and titanium dioxide.

5.2.1.2. Dolutegravir (DTG) 50 mg and Placebo to Match Tablets

Dolutegravir 50 mg tablets are round, film-coated yellow, debossed with "50" on one side and debossed with "SV 572" on the other side. Each tablet core contains 50 mg of dolutegravir. In addition to the active ingredient, DTG tablets contain D-mannitol, microcrystalline cellulose, povidone K29/32, sodium starch glycolate and sodium stearyl fumarate. The tablet cores are film-coated with iron oxide yellow, polyethylene glycol, polyvinyl alcohol, talc and titanium dioxide.

The placebo to match (PTM) DTG tablets are round, film coated yellow, debossed with "50" on one side and debossed with "SV 572" on the other side. PTM DTG tablets are identical in physical appearance to DTG 50 mg tablets. The placebo tablet cores contain microcrystalline cellulose, lactose monohydrate, croscarmellose sodium and magnesium stearate. The tablet cores are film-coated with iron oxide yellow, polyethylene glycol, polyvinyl alcohol, talc and titanium dioxide.

5.2.1.3. Emtricitabine/Tenofovir alafenamide (F/TAF) 200 mg/25 mg and Placebo to Match Tablets

Emtricitabine 200 mg/tenofovir alafenamide 25 mg tablets are rectangular-shaped, film-coated blue, debossed with "GSI" on one side of the tablet and "225" on the other side of the tablet. Each tablet core contains 200 mg of emtricitabine and 25 mg of tenofovir alafenamide. In addition to the active ingredients, the F/TAF tablets contain croscarmellose sodium, magnesium stearate and microcrystalline cellulose. The tablet cores are film-coated with FD&C blue #2/indigo carmine aluminum lake, polyethylene glycol, polyvinyl alcohol, talc and titanium dioxide.

The placebo to match (PTM) F/TAF tablets are rectangular-shaped, film-coated blue, debossed with "GSI" on one side of the tablet and "225" on the other side of the tablet. PTM F/TAF tablets are identical in physical appearance to F/TAF 200 mg/25 mg tablets. The placebo tablet cores contain microcrystalline cellulose, lactose monohydrate, croscarmellose sodium and magnesium stearate. The tablet cores are film-coated with FD&C blue #2/indigo carmine aluminum lake, polyethylene glycol, polyvinyl alcohol, talc and titanium dioxide.

5.2.2. Packaging and Labeling

5.2.2.1. GS-9883/Emtricitabine/Tenofovir alafenamide (GS-9883/F/TAF) 50 mg/200 mg /25 mg and Placebo to Match Tablets

GS-9883/F/TAF tablets and PTM GS-9883/F/TAF tablets are packaged in white, high density polyethylene (HDPE) bottles. Each bottle contains 30 tablets, silica gel desiccant and polyester packing material. Each bottle is enclosed with a white, continuous thread, child-resistant polypropylene screw cap with an induction-sealed and aluminum-faced liner.

Study drug(s) to be distributed to centers in the US and other participating countries shall be labeled to meet applicable requirements of the US FDA, EU Guideline to Good Manufacturing Practice - Annex 13 (Investigational Medicinal Products), and/or other local regulations.

5.2.2.2. Dolutegravir (DTG) 50 mg and Placebo to Match Tablets

Dolutegravir 50 mg tablets and PTM Dolutegravir 50 mg tablets are packaged in white, high density polyethylene (HDPE) bottles. Each bottle contains 30 tablets. Each bottle is enclosed with a white, continuous thread, child-resistant polypropylene screw cap with an induction-sealed and aluminum-faced liner.

Study drug(s) to be distributed to centers in the US and other participating countries shall be labeled to meet applicable requirements of the US FDA, EU Guideline to Good Manufacturing Practice - Annex 13 (Investigational Medicinal Products), and/or other local regulations.

5.2.2.3. Emtricitabine/Tenofovir Alafenamide (F/TAF) 200 mg/25 mg and Placebo to Match Tablets

Emtricitabine/tenofovir alafenamide (F/TAF) 200 mg/25 mg and Placebo to Match tablets are packaged in white, high density polyethylene (HDPE) bottles. Each bottle contains 30 tablets, silica gel desiccant, and polyester packing material. Each bottle is enclosed with a white, continuous thread, child-resistant polypropylene screw cap with an induction-sealed and aluminum-faced liner.

Study drug(s) to be distributed to centers in the US and other participating countries shall be labeled to meet applicable requirements of the US FDA, EU Guideline to Good Manufacturing Practice - Annex 13 (Investigational Medicinal Products), and/or other local regulations.

5.2.3. Storage and Handling

Study drugs should be stored at controlled room temperature of 25°C (77°F); excursions are permitted between 15°C and 30°C (59°F and 86°F). Storage conditions are specified on the label. Until dispensed to the subjects, all bottles of study drugs should be stored in a securely locked area, accessible only to authorized site personnel.

To ensure the stability and proper identification, study drug(s) should not be stored in a container other than the container in which they were supplied.

Consideration should be given to handling, preparation, and disposal through measures that minimize drug contact with the body. Appropriate precautions should be followed to avoid direct eye contact or exposure through inhalation when handling.

5.3. Dosage and Administration of GS-9883/Emtricitabine/Tenofovir alafenamide and Dolutegravir + Emtricitabine/Tenofovir alafenamide

Study drugs GS-9883/F/TAF FDC, DTG + F/TAF FDC and placebo-to-match tablets will be provided by Gilead Sciences.

Treatment Group 1: FDC of GS-9883 50 mg/emtricitabine 200 mg/ tenofovir alafenamide 25 mg (GS-9883/F/TAF) + Placebo to match dolutegravir 50 mg and Placebo to match FDC of emtricitabine 200 mg/tenofovir alafenamide 25 mg (F/TAF) administered orally, once daily, without regard to food

Treatment Group 2: Dolutegravir 50 mg + FDC of emtricitabine 200 mg/tenofovir alafenamide 25 mg (F/TAF) + Placebo to match FDC of GS-9883 50 mg/emtricitabine 200 mg/tenofovir alafenamide 25 mg (GS-9883/F/TAF) administered orally, once daily, without regard to food.

After the End of Blinded Treatment Visit, all subjects who choose to participate in the open-label extension will receive GS-9883/F/TAF FDC once daily

Subjects will be instructed to bring all study medication in the original container at each clinic visit for drug accountability. The Investigator will be responsible for maintaining accurate records for all study drug bottles dispensed and tablets returned. The inventory and dispensing logs must be available for inspection by the study monitor. Study medication supplies, including partially used or empty bottles, must be accounted for by the study monitor prior to destruction or return.

5.4. Prior and Concomitant Medications

5.4.1. Prior and Concomitant Medications (Blinded Phase through End of Blinded Treatment Visit)

The use of medications for the treatment of HIV, other than study drug, is prohibited.

Medications listed in the following table and use of herbal/natural supplements are excluded or should be used with caution while subjects are participating in the study. Subjects will refrain from consumption of grapefruit juice and Seville orange juice throughout participation in the study.

Table 5-1. Prior and Concomitant Medications (Blinded Phase through End of Blinded Treatment Visit)

Drug Class	Agents Disallowed*	Use Discouraged and To Be Used With Caution
Acid Reducing Agents Antacids Buffered medications		Concentration of study drug may decrease with antacids. Subjects may not take antacids (eg, Tums or Roloids); the ulcer medication sucralfate (Carafate); or vitamin or mineral supplements that contain calcium, iron or zinc for a minimum of 6 hours before and 2 hours after any dose of study drug.
Antiarrhythmic Agent	Dofetilide	
Anticonvulsants	Phenobarbital, Phenytoin, Carbamazepine, Oxcarbazepine	
Antimycobacterials	Rifampin, Rifapentine	
Antiretrovirals	Any antiretroviral drug that is not part of the study regimen	
GI Motility Agents	Cisapride	
Herbal/Natural Supplements	St. John's Wort, Echinacea	
Oral Hypoglycemic Agent		Metformin: close monitoring is recommended. A dose adjustment of Metformin may be necessary. Limit total daily doses of Metformin to 1000 mg when initiating study medication or if initiating metformin while on study drug.

* Administration of any of the above medications must be discontinued at least 30 days prior to the Day 1 visit and for the duration of the study.

Should subjects have a need to initiate treatment with any excluded concomitant medication, the Gilead Sciences Medical Monitor must be consulted prior to initiation of the new medication. In instances where an excluded medication is initiated prior to discussion with the Sponsor, the Investigator must notify Gilead Sciences as soon as he/she is aware of the use of the excluded medication.

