5.4.2. Prior and Concomitant Medications (Open-Label Rollover Extension Phase)

The use of medications for the treatment of HIV-1 infection, other than GS-9883/F/TAF, is prohibited.

Medications listed in the following table and use of herbal/natural supplements are excluded or should be used with caution while participants are participating in the study. This list should be utilized in jurisdictions in which GS-9883/F/TAF has NOT been approved.

Table 5-2. Prior and Concomitant Medications (Open-Label Rollover Extension Phase)

Drug Class	Agents Disallowed*	To Be Used With Caution
Medications or oral supplements containing polyvalent cations (e.g., Mg, Al, Ca, Fe): Calcium or iron supplements Cation-containing antacids or laxatives Buffered medications		Antacids containing Al/Mg or Calcium: GS-9883/F/TAF can be taken under fasting conditions 2 hours before antacids containing Al/Mg or calcium. Routine administration of GS-9883/F/TAF simultaneously with, or 2 hours after, antacids containing Al/Mg or calcium is not recommended. Supplements containing Calcium or Iron: GS-9883/F/TAF and supplements containing calcium or iron can be taken together with food. Routine administration of GS-9883/F/TAF under fasting conditions simultaneously with, or 2 hours after, supplements containing calcium or iron is not recommended.
Antiarrhythmic Agent	dofetilide	
Anticonvulsants	phenobarbital, phenytoin, carbamazepine, oxcarbazepine	
Antimycobacterials	rifampin, rifapentine, rifabutin	
Antiretrovirals	Any antiretroviral drug that is not part of the study regimen	
Hypoglycemic agent		Metformin: Refer to the prescribing information of metformin for assessing the benefit and risk of concomitant use of BIKTARVY and metformin.
Herbal/Natural Supplements	St. John's Wort	

* Administration of any of the above medications must be discontinued at least 30 days prior to the Day 1 visit and for the duration of the study.

In jurisdictions in which GS-9883/F/TAF has been approved, consult the local prescribing information for GS-9883/F/TAF dose recommendations with concomitant medications.

Should participants have a need to initiate treatment with any excluded concomitant medication, the Gilead Medical Monitor must be consulted prior to initiation of the new medication. In instances where an excluded medication is initiated prior to discussion with the Sponsor, the Investigator must notify Gilead as soon as he/she is aware of the use of the excluded medication.

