8.5.1.2. US FDA-defined Snapshot Algorithm

The analysis window at Week 48 is defined as from Study Day 295 to Study Day 378. All HIV-1 RNA data collected on-treatment (ie, including data collected up to 1 day after the last dose date of study drug) will be used in the snapshot algorithm. Virologic outcome will be defined as the following categories:

- **HIV-1 RNA < 50 copies/mL:** this includes subjects who have the last available HIV-1 RNA < 50 copies/mL in the Week 48 analysis window while on randomized treatment
- **HIV-1 RNA ≥ 50 copies/mL:** this includes subjects
 - a) Who have the last available HIV-1 RNA ≥ 50 copies/mL in the Week 48 analysis window while on randomized treatment, or
 - b) Who do not have on-treatment HIV-1 RNA data in the Week 48 analysis window and
 - i) Who discontinue study drug prior to or in the Week 48 analysis window due to lack of efficacy, or
 - ii) Who discontinue study drug prior to or in the Week 48 analysis window due to reasons other than adverse event (AE), death, or lack of efficacy and have the last available HIV-1 RNA up to 1 day after the premature discontinuation of the study drug ≥ 50 copies/mL

- **No Virologic Data in the Week 48 analysis window:** this includes subjects who do not have on-treatment HIV-1 RNA data in the Week 48 analysis window because of the following:
 - a) Discontinuation of study drug prior to or in the Week 48 analysis window due to AE or death (regardless of whether the last available HIV-1 RNA up to 1 day after the premature discontinuation of the study drug < 50 copies/mL or not) or,
 - b) Discontinuation of study drug prior to or in the Week 48 analysis window due to reasons other than AE, death, or lack of efficacy (eg, withdrew consent and loss to follow-up) and the last available HIV-1 RNA up to 1 day after the premature discontinuation of the study drug < 50 copies/mL or,
 - c) Missing data during the window but on study drug.

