6.3.2. Analysis of the Efficacy Endpoints for All B/F/TAF Analysis

6.3.2.1. Analysis of the Proportion of Subjects with HIV-1 RNA < 50 copies/mL by and Missing = Excluded and Missing = Failure Approaches

The proportion of subjects with HIV-1 RNA < 50 copies/mL will be analyzed using M = E for imputing missing HIV-1 RNA values using the All B/F/TAF Analysis Set for the all B/F/TAF analysis.

- Missing = Excluded (M = E)

In this approach, all missing data will be excluded in the computation of the percentages (ie, missing data points will be excluded from both the numerator and denominator in the computation). The denominator for percentages at a visit is the number of subjects in the all B/F/TAF analysis set with nonmissing HIV-1 RNA value at that visit.

- Missing = Failure (M = F)

In this approach, all missing data will be treated as HIV-1 RNA \geq 50 copies/mL. The denominator for percentages is the number of subjects in all B/F/TAF analysis set.

For M = E and M=F analyses, the number and percentage of subjects with HIV-1 RNA in the following categories will be summarized:

- < 50 copies/mL
 - < 20 copies/mL
 - < 20 copies/mL Not Detectable
 - < 20 copies/mL Detectable
 - 20 to < 50 copies/mL

- 50 to < 200 copies/mL
- 200 to < 400 copies/mL
- 400 to < 1000 copies/mL
- ≥ 1000 copies/mL
- Missing (only applicable for M=F analysis)

For all B/F/TAF analyses, the 95% CI for the proportion of subjects with HIV-1 RNA < 50 copies/mL for a treatment group will be constructed using the Clopper-Pearson exact method.

For M =F analysis, results will be summarized by visit up to Week 240 for B/F/TAF group and up to Week 96 for DTG + F/TAF to B/F/TAF group. For the M = E analysis, results will be summarized by treatment group for all visits through the end of study. No statistical comparison will be made for the all B/F/TAF analysis.

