7.4. Prior and Concomitant Medications

7.4.1. Nonstudy Drug Antiretroviral Medications

Any nonstudy drug ARV medications used prior to, during, or after the study (if collected) will be coded using the Gilead-modified World Health Organization (WHO) Drug Dictionary for ARV medications. The WHO preferred drug name and drug code will be attached to the clinical database. All nonstudy drug ARV medications will be listed. No inferential statistics will be provided.

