Yes	Yes	-	-	Compare post-BL Urine RBC (Quant.) toxicity grade to BL Urine RBC (Quant.) toxicity grade. If post-BL toxicity is greater than BL toxicity, then treatment-emergent
Yes	No	-	-	Treatment-emergent. Use post-BL Urine RBC (Quant.) toxicity grade.
No	-	Yes	Yes	Compare post-BL Urine Blood (Dipstick) toxicity grade to BL Urine Blood (Dipstick) toxicity grade. If post-BL toxicity is greater than BL toxicity, then treatment-emergent
No	-	Yes	No	Treatment-emergent. Use post-BL Urine Blood (Dipstick) toxicity grade.
No	-	No	-	Do not count subject in the denominator for “Urine RBC (Hematuria, Quantitative or Dipstick)”

BL = Baseline. Quant = Quantitative. “-” means any value can be present (or it can be missing), as it does not affect the classification

16) Concomitant nonstudy-drug ARV medications for all B/F/TAF analysis (ie, ARV medications other than study drug that are taken while receiving study drug B/F/TAF) will be flagged in “Nonstudy-Drug Antiviral Medication” listing. The logic to define concomitant nonstudy-drug ARV is similar to concomitant non-ARV Medications (see details in Section 7.4.2)

17) Lipid modifying medication analyses for All B/F/TAF analysis:

Lipid modifying medication is defined to be the concomitant medication with ATC2 term = “LIPID MODIFYING AGENTS” and CMDECOD contains wording of “STATIN” in the ADCM dataset.

Subjects who took lipid-modifying medications at the first dose of B/F/TAF (including both phases) refer to the subjects who use of the lipid-modifying agents at study day 1 of all B/F/TAF analysis. More specifically, subjects with “Lipid Modifying Agent Use at the first dose of B/F/TAF” include those subjects in All B/F/TAF Analysis Set with: 1) any selected CM record with the start date ≤ the first dose date of B/F/TAF (including both phases), and 2) the end date of the selected CM record is ongoing or the end date of the selected CM record ≥ the first dose date of B/F/TAF (including both phases).

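### HIV-1 RNA below 50 copies/mL on a non-study antiretroviral counts as B/F/TAF success under the SAP's M=E and M=F rules; the protocol snapshot has a narrower form of the same gap

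*Protocol*

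**What the plan says.** **Prohibition.** Protocol 5.4.1 covers the blinded phase: "The use of medications for the treatment of HIV, other than study drug, is prohibited". Protocol 5.4.2 covers the extension: "The use of medications for the treatment of HIV-1 infection, other than GS-9883/F/TAF, is prohibited". For a subject who needs an excluded drug, the written consequence is that "the Gilead Sciences Medical Monitor must be consulted prior to initiation of the new medication", or that the sponsor is notified afterwards. Neither section says how later HIV-1 RNA is scored.

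**Snapshot (protocol 8.5.1.2).** Eligible data are defined as follows: "All HIV-1 RNA data collected on-treatment (ie, including data collected up to 1 day after the last dose date of study drug"). For success, the text reads: "this includes subjects who have the last available HIV-1 RNA < 50 copies/mL in the Week 48 analysis window while on randomized treatment". None of the categories for 50 copies/mL or more, or for no virologic data, mentions another ARV.

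**M=E and M=F (SAP 6.3.2.1).** For M=E: "The denominator for percentages at a visit is the number of subjects in the all B/F/TAF analysis set with nonmissing HIV-1 RNA value". M=F turns only missing values into failures. SAP 3.1.2 brings in all efficacy data collected for the All B/F/TAF analysis. SAP 3 brings in all available data for subjects who received B/F/TAF in the randomized phase. SAP 6.3.2.2 limits CD4 to data up to 1 day after the last dose; 6.3.2.1 has no such limit for HIV-1 RNA.

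**Use of the ARV data.** SAP 7.4.1: "All nonstudy drug ARV medications will be listed. No inferential statistics will be provided". SAP Appendix 6, item 16: "ARV medications other than study drug that are taken while receiving study drug B/F/TAF) will be flagged in" a listing. No efficacy rule uses the flag.

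**The concern.** The All B/F/TAF proportions are meant to describe suppression on B/F/TAF, and the snapshot is meant to describe suppression on the randomized regimen. If a value is below 50 copies/mL while the subject takes another ARV, part or all of the suppression may come from that drug. Counting it as success can only hold the rate up or raise it.

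In the single-arm long-term results this is an upward bias. In the randomized comparison, rescue in both arms pulls a worse arm toward a better one, which is the anti-conservative direction for non-inferiority.

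**Working it through.** **Which cases each written rule scores as success**

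1. *ARV added while study drug continues, HIV-1 RNA below 50.* The snapshot fixes on-treatment status by the date of the last study-drug dose plus 1 day, so the value is eligible and is a success in the full analysis set. In M=E and M=F the value is nonmissing and below 50, so it is a success there too.
2. *B/F/TAF stopped in the blinded phase, replacement regimen started, HIV-1 RNA below 50.* Protocol 6.6.1 asks such subjects to keep attending visits through the End of Blinded Treatment Visit. Note e to Figure 6-1 foresees a new ARV regimen with the subject remaining in the study. The snapshot drops values more than 1 day after the last dose. SAP 6.3.2.1 does not, so the value is a B/F/TAF success, even in M=F.

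**The plan's own figure.** Inputs from protocol 8.9: 300 per arm, 91% response in both arms, margin 12 points, one-sided 0.025.

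- SE = sqrt(2 × 0.91 × 0.09 / 300) = 0.02337
- Power = Φ(0.12/0.02337 − 1.96) = 99.93%, consistent with the stated minimum of 95%
- 95% CI half-width = 1.96 × 0.02337 = 4.58 points

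**Effect of one case.** No count is given, so 1 to 5 cases are assumed, starting from 273/300 = 91.00%.

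| Cases | Scored as failure (M=F, snapshot) | Excluded (M=E) |
|---|---|---|
| 1 | 272/300 = 90.67%, down 0.33 | 272/299 = 90.97%, down 0.03 |
| 5 | 268/300 = 89.33%, down 1.67 | 268/295 = 90.85%, down 0.15 |

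The size of the group switching from DTG + F/TAF is not given. If it were 250 (assumed), one case would be 1/250 = 0.40 points in M=F.

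**Could the primary conclusion change?** Take 273/300 in both arms, and two-sided alpha 0.05 − 2 × 0.00001 = 0.04998 (two planned IDMC reviews, protocol 8.10). Use an unstratified interval and rescore k subjects in the GS-9883 arm only:

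| k | Difference (points) | Lower bound (points) |
|---|---|---|
| 0 | 0.00 | −4.58 |
| 3 | −1.00 | −5.69 |
| 9 | −3.00 | −7.90 |
| 20 | −6.67 | −11.90 |
| 21 | −7.00 | −12.26 |

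It takes 21 subjects, 7.0% of one arm and none in the other, to pass −12. Rescoring 3 to 15 in each arm leaves the difference at 0 and the lower bound between −4.80 and −5.55.

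**Direction at the margin.** Let the true rates be 79% and 91%, and let a share f of would-be failures in both arms be suppressed by an added ARV. For f = 5%, the scored rates are 0.79 + 0.05 × 0.21 = 0.8005 and 0.91 + 0.05 × 0.09 = 0.9145. The apparent difference is −11.4 points, and the chance of declaring non-inferiority rises from 0.025 to 0.040. That is about 3 subjects (0.05 × 63) and 1 subject (0.05 × 27). For f = 2% it is 0.030 and for f = 10% it is 0.064.

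**The case against.** **Earlier SAPs.** SAP 6.1 and 6.2.1 place the snapshot methods in the Week 48 and other interim SAPs, and SAP 6.1 cites a guidance for the algorithm. None of these is available here. A reader might infer that no analysis anywhere scores the case as failure. The documents do not support that: such a rule can be neither confirmed nor excluded. SAP 6 also says the randomized-phase analyses are complete and will not be repeated. This stands, and it makes SAP 6.3.2.1 the main target.

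**Per-protocol set.** Protocol 8.2.1.2.2 drops major violators and subjects meeting the Section 4.3 ongoing-therapy criterion. That table includes non-study ARVs, with a footnote that runs for the whole study. The protection is real but partial. The set is secondary, its listed exclusions are for Week 48, it removes subjects rather than scoring failures, and the criterion is worded for entry. The final SAP defines no such set.

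**On-drug wording.** SAP 3 opens by describing the All B/F/TAF data, as an example, as data collected while participants were on B/F/TAF. That suggests an on-treatment intent. The bullets that define the data then admit everything available, and only CD4 carries an explicit cut-off, so the intent is not written into the HIV-1 RNA rule.

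**No rescue pathway.** The rebound schema has subjects stay on study drug or stop it; no add-on branch is written. Item 16 is a routine listing flag, so it does not show that the sponsor expected add-on rescue. This stands for added ARVs. It does not touch the replacement-regimen case, which the schema itself foresees.

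**Choice of estimand.** M=E and M=F are missing-data rules, and recoding an observed value changes what is estimated. That is fair, but the choice should then be stated and the affected subjects counted.

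**Risk in the flag.** Item 16 borrows the SAP 7.4.2 logic. That logic accepts a start on the last-dose day and resolves incomplete dates by month or year. A suppressed completer moving to commercial treatment after Week 96 OL could be flagged and wrongly scored as a failure. This stands, and the fix needs safeguards.

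**Conclusion.** The gap is in the written rules. SAP 6.3.2.1 credits B/F/TAF with suppression on an added ARV and on a replacement regimen, in M=E and in M=F. Protocol 8.5.1.2 does so only for an ARV added while study drug continues.

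The size is unknown. Each case is worth at most 0.33 points in an arm of 300, and nothing if that subject would have been below 50 copies/mL anyway. A reader might take 0.3 to 1.7 points as the actual overstatement. That would require 1 to 5 cases in one arm, all otherwise at 50 or above, and the documents give no such count. A reader might also infer that the non-inferiority result is in doubt. Under the planning rates, and with an unstratified interval, that takes 21 one-sided cases, so a reversal is unlikely.

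The change is worth making because the final analysis rests on SAP 6.3.2.1 and the ARV data are already collected.

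**What to change.** **SAP 6.3.2.1**

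- Restrict HIV-1 RNA to on-treatment values, up to 1 day after the last B/F/TAF dose, as for CD4.
- If the selected value was sampled while a non-study ARV was being taken, count it as 50 copies/mL or more in M=F and exclude it in M=E.
- Apply this only if the ARV start date is before the sample date and the ARV is not the transition to commercial treatment at or after the last dose. Do not apply it on an imputed month- or year-level date alone.
- Report the number of affected subjects by group.

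**Protocol 8.5.1.2.** Add the same condition to the category of 50 copies/mL or more. Alternatively, since those analyses are complete, report affected subjects by arm with a sensitivity analysis that scores them as 50 copies/mL or more.

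**Cost.** A few sentences, a flag the SAP already derives, and one date check. The downside is a slightly lower reported response rate. If the SAP is already final, SAP 1 provides for recording the change in the study report. None of this alters how subjects are treated.
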